### **Exploratory Endpoints**

1. Inflammation markers including: IL-6, CRP, IL-10, TNF- $\alpha$ , IFN- $\gamma$ , IFN- $\alpha$ , IP-10, MCP-1, CD4+ and CD8+ T cells, and absolute lymphocyte count
2. Assess peak and trough concentrations of asapiprant at steady state
3. Assess PGD2 pre-diagnostic to assess correlation with response to treatment for COVID-19 based on change in the WHO Ordinal Scale for COVID-19 score

### **Safety Analysis:**

Safety endpoints:

1. Incidence and severity of treatment-emergent AEs
2. Safety outcome measure:
  - a. Occurrence of AEs
  - b. Laboratory safety parameters such as complete blood count, blood glucose, electrolyte, hepatic and renal functions taken before the first dose and on Days 2, 5, 14, 28 and the time of discharge to find any changes or any systemic effect after treatment

All AEs will be coded using the Medical Dictionary for Regulatory Activities (MedDRA) Version 23.1. The incidence of all AEs reported during the study will be summarized by treatment group and system organ class and preferred term. Safety will be evaluated by comparing the nature, severity, and frequency of AEs between/among the treatment groups.

**Safety Monitoring:** Study Investigators will monitor subject safety on an ongoing basis while hospitalized, including a review of vital signs, local safety laboratory measurements, and observations of subject status. If discharged prior to the end of treatment, subjects will be discharged to home, and home health resources will be utilized to manage daily subject dosing and status, including the collection of protocol-specified laboratory tests and assessments. The home assessments will be monitored by the study Investigator.

BioAge Labs will have a blinded Medical Lead assigned for safety oversight and will work closely with a contract research organization (CRO) partner to provide ongoing reviews of

subject safety data, including findings associated with laboratory tests, electrocardiograms (ECGs), vital signs, physical examinations, and AE. Routine Medical Monitor review will be conducted on an ongoing basis during study conduct. The CRO will provide a drug safety team to manage serious adverse event reporting.

An IA for efficacy will be planned when 208 subjects complete study assessments through the 28-day follow up (Day 28) approximately 14 days after the final dose of study drug.

An independent Data Monitoring Committee (DMC) will be utilized during the study to monitor subject safety throughout study conduct. A DMC charter will be developed before study initiation and will define DMC processes and meetings. The DMC will meet at regular planned intervals during study conduct and also meet ad hoc as required for any identified urgent safety findings. Independent of the Sponsor, the DMC will be responsible for performing the IA and evaluating the interim results.

To aid the DMC in their recommendation to BioAge regarding conduct of the trial beyond the IA, a table of multiple possible true effects and potential stopping rules will be developed by BioAge and presented in the DMC charter. The operating characteristics of potential decision rules will be shared and understood by the DMC.

**Interim Analysis:** An IA is planned when approximately 208 subjects complete study assessments through the 28-day follow up (Day 28) approximately 14 days after the final dose of study drug.

**Table 1: Schedule of Assessments**

	Screening	Baseline	Treatment													Time of Discharge a	28-Day Follow-up	End of Study Follow-up
Study Day (Window)	Day -3 to -1	Day 1	2	3	4	5 + 2	6	7	8	9	10	11	12	13	14/ EOT + 2		Day 28 (±2 days)	Day 57 (±4 days)
Informed consent	X																	
Inclusion/exclusion criteria review	X	X																
Medical history/ demographics	X																	
Physical examination b	X																	
Abbreviated physical examination b					X										X	X	X	
Vital signs b	X	X	X	X	X	X	X	X	X	X	X	X	X	X	X	X	X	
Prior medication review	X																	
Safety laboratory tests	X i		X		X										X	X	X	
O 2 Saturation/ FiO 2	X	X	X	X	X	X	X	X	X	X	X	X	X	X	X	X	X	
WHO Ordinal Scale for COVID-19 c	X	X	X	X	X	X	X	X	X	X	X	X	X	X	X	X	X	X
12-Lead ECG		X	X												X e	X e		
Concomitant medication review	X	X	X	X	X	X	X	X	X	X	X	X	X	X	X	X	X	X
Assessment for AEs		X	X	X	X	X	X	X	X	X	X	X	X	X	X	X	X	X
Randomization		X																
Dosing		X	X	X	X	X	X	X	X	X	X	X	X	X	X			
PK peak g		X			X										X e	X f		

	Screening	Baseline	Treatment													Time of Discharge a	28-Day Follow-up	End of Study Follow-up
Study Day (Window)	Day -3 to -1	Day 1	2	3	4	5	6	7	8	9	10	11	12	13	14/ EOT + 2		Day 28 (±2 days)	Day 57 (±4 days)
			X (Collect PK sample following first NG dosing, if applicable)															
PK trough d, e, f						X									X e	X f		
PGD2 pre-diagnostic sample collection		X																
Viral titers nasopharyngeal h	X	X	X	X	X	X	X	X	X	X	X					X		
Blood for inflammation markers	X		X		X										X	X		
Proteomic, metabolomics, and transcriptomic sample collection		X													X			

Abbreviations: AE = adverse event; FiO2 = fractional inspired oxygen; ECG = electrocardiogram; EOT = end of treatment; NG = nasogastric tube; O2 = oxygen; PGD2 = prostaglandin D2; PK = pharmacokinetic(s)

a Visit procedures at time of discharge will occur at the date of the dosing visit if visit occurs prior to Day 14, will occur at the Day 14 visit if occurs on Day 14, or will occur on the date of discharge after dosing if after Day 14. This visit is not required if discharge occurs within 2 days after Day 14. If discharge occurs on Day 4, the Day 5 assessments of abbreviated physical exam, safety labs, trough and peak PK, and blood for inflammation markers will not be collected if they were completed as part of the discharge procedures on Day 4.

b Same-day medical record examinations may be used for study purposes to reduce the possible exposure of site staff to COVID-19 risk. Physical examinations may be conducted as standard of care examinations. Abbreviated physical examinations may be conducted by qualified home health care providers or remote/telemedicine visits. Abbreviated physical examinations that cannot be performed at day 5 may be performed up to Day 7.

c WHO Ordinal Scale is derived from subject's oxygen supplementation requirements, hypotension or need for vasopressors, need for renal dialysis, and activity limitations for outpatients.

d Trough PK samples collected within 30 minutes prior to dose.

e ECG and PK sampling to be performed on last day of study treatment if subject remains hospitalized through Day 14. ECG and PK samples are not required on Day 14/EOT if subject is discharged to home before Day 14.

f ECG and PK sampling to be performed at the time of hospital discharge if subject is discharged prior to Day 14. ECG and PK sampling are not required at time of discharge if discharge occurs after the Day 14 visit.

g Peak PK samples collected 3-6 hours after dose.

h Done every other day until 2 qualitative test done at local laboratory is negative. After qualitative test is negative, do viral titer nasopharyngeal testing only on Day 28. For outpatients, scheduled viral titer tests may be skipped on Saturday or Sunday and/or may be skipped if dry ice shipments are not available. In the Saturday or Sunday situation Day 13 tests should be done on the following Monday.

i Safety labs collected within 48 hours prior to consent as part of standard of care can be used to confirm eligibility.

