### 2.3.2 Secondary Endpoints

1. Safety as assessed by adverse events (AEs) as measured by the Common Terminology Criteria for Adverse Events (CTCAE) v 5.0
2. Proportion of subjects surviving [Time Frame: at Day 14, at Day 28, at Day 57]
3. Proportion of subjects who survive without progression to RF [Time Frame: at Day 14, at Day 28, at Day 57]
4. Time to two successive negative viral titers in nasopharyngeal swab
5. Time to clinical worsening from baseline value (defined by time to  $\geq$  1-point worsening on the World Health Organization (WHO) Ordinal Scale for COVID-19 [[Table 2](#)]):

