### **7.2.8 Nasopharyngeal Viral Titers**

Nasopharyngeal swabs for quantitative viral titer assessments will be collected at the times specified in [Table 1](#) by appropriately delegated study staff. These nasopharyngeal swabs will be completed every other day until two confirmed negative qualitative tests are obtained.

Qualitative COVID-19 tests are not required and may be elected by the subject and Investigator. Qualitative tests are performed at the site's local laboratory. When a qualitative negative result is confirmed (two consecutive tests are negative), the site will verify that a final quantitative nasopharyngeal swab has been collected for at least one visit following the first qualitative negative result. The study laboratory manual will outline proper sample handling for quantitative viral titer assessments. Qualitative testing will be performed per the site's local laboratory standard testing procedures.

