10.2.2 Time to event endpoints

Following time to event endpoints will be presented by treatment group, using the Kaplan-Meier estimator. A Cox proportional hazards model with treatment, previous COVID-19 therapy (yes/no), region, and age group (50 to < 75 vs. ≥ 75 years of age) as covariates will be used to estimate the hazard ratio and compare treatment groups. In addition, the log rank test and stratified log rank test, with age group and region as the strata, will be provided.

- Time to two successive negative viral titers in nasopharyngeal swab: which is defined as time from the date of randomization to the date of second post-dosing viral titers collection with negative result of two successive negative viral titers tests. If a patient doesn't have documented two successive negative viral titers, it will be censored at the date of Day 28 or date of discontinuation from study, which ever comes earlier.
- Time to clinical worsening from baseline value (defined by time to ≥ 1 -point worsening on WHO Ordinal Scale for COVID-19): which is defined as time from the date of randomization to the date of first post-dosing collection of WHO Ordinal Scale for COVID-19 showing higher than baseline, i.e., ≥ 1 -point worsening. If a patient doesn't have documented worsening post-baseline WHO Ordinal Scale, it will be censored at the date of Day 57 or date of discontinuation from study, which ever comes earlier.
- Time to clinical improvement from baseline value (defined by time to ≥ 1 -point improvement on WHO Ordinal Scale for COVID-19 score – must be maintained through Day 28): which is defined as time from the date of randomization to the date of first post-dosing collection of WHO Ordinal Scale for COVID-19 showing a decrease from baseline, i.e., ≥ 1 -point decrease demonstrating clinical improvement. If a patient doesn't have documented improving post-baseline WHO Ordinal Scale, it will be censored at the date of Day 28 (including death prior to Day 28) or date of discontinuation from study, whichever comes earlier.

10.2.3 Mean change in WHO Ordinal Scale for COVID-19 score at Day 14/End of Treatment, Day 28, Day 57

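### Optional local negatives can stop the quantitative swabs after one negative titer, and SAP 10.2.2 then dates an early viral clearance at Day 28

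*Protocol*

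**What the plan says.** Protocol 2.3.2 lists as a secondary endpoint "Time to two successive negative viral titers in nasopharyngeal swab". It serves the first secondary objective, faster viral clearance.

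SAP 10.2.2 counts from randomization to the "date of second post-dosing viral titers collection with negative result of two successive negative viral titers tests". Without such a pair, "it will be censored at the date of Day 28 or date of discontinuation from study, which ever comes earlier". Local qualitative results play no part in the definition.

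Swab collection, however, is governed by those local results:

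- Footnote h, first sentence: "Done every other day until 2 qualitative test done at local laboratory is negative".
- Footnote h, second sentence: "After qualitative test is negative, do viral titer nasopharyngeal testing only on Day 28".
- Protocol 7.2.8: "These nasopharyngeal swabs will be completed every other day until two confirmed negative qualitative tests are obtained". After two local negatives in a row, "the site will verify that a final quantitative nasopharyngeal swab has been collected for at least one visit following the first qualitative negative result".

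Section 7.2.8 also makes local testing optional. Footnote h lets outpatients skip weekend swabs, and swabs for which no dry ice shipment is available.

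**The concern.** The rule that ends sampling and the rule that defines the event use different assays. The event needs two negative titers. The protocol guarantees only one quantitative swab after the first local negative, and that swab may be the first negative titer. The next scheduled titer is then on Day 28, and the SAP places the event there.

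Sampling stops because the subject appears to have cleared the virus, so the displacement falls on early clearers. At stake are the recorded clearance times, the Kaplan-Meier curves and medians and, to a lesser degree, the estimated treatment effect on this endpoint.

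**Working it through.** The plan states no figure for this endpoint, so there is none to reproduce. I followed the rules through and then sized the effect under stated assumptions.

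**1. A sequence that complies with every rule.** Titer positive on Day 5; local tests negative on Days 6 and 7; titer negative on Day 7, which is a quantitative swab after the first local negative as 7.2.8 asks; swabs stop; next titer on Day 28. The recorded event is Day 28. Had swabs continued, the second negative would have been on Day 9. The delay is 28 − 9 = 19 days. If the Day 28 swab is missed, the subject is censored.

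**2. How often the rules produce this.** Assumptions not in the documents: post-dose swabs on Days 3, 5, 7, 9, 11 and 13, then Day 28; first possible local negative on each of Days 2 to 11 (ten cases). With uninterrupted swabs and agreeing assays, every case is recorded between Day 5 and Day 13. With early stopping:

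- Stop at two local negatives plus the 7.2.8 swab, local tests daily, assays agreeing: 5 of 10 cases (Days 2, 4, 6, 8, 10) go to Day 28.
- Same rule, local tests on swab days, assays agreeing: no delay in any case.
- Same rule, local tests on swab days, titer turning negative two days after the local test: all 10 are recorded at Day 28. Two of these (Days 10 and 11) would be at Day 28 even with uninterrupted swabs.
- Stop at the first local negative (footnote h, second sentence, read literally), local tests daily or on swab days, assays agreeing: all 10 are recorded at Day 28 or censored there.

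**3. Effect on medians.** Assume exponential clearance from Day 1 with means of 10 days (asapiprant) and 14 days (placebo), the same swab days, agreeing assays and no missed Day 28 swab. The proportion with a negative titer by swab day d is F(d) = 1 − exp(−(d − 1)/mean).

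| By swab day | Mean 10 | Mean 14 |
|---|---|---|
| 7 | 0.451 | 0.349 |
| 9 | 0.551 | 0.435 |
| 11 | 0.632 | 0.511 |
| 13 | 0.699 | 0.576 |

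Dated at the second negative, the event comes one swab later. The curves pass 50% at Day 11 (F(9) = 0.551) and Day 13 (F(11) = 0.511), so the medians are 11 vs 13.

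Now let a share s of early clearers (first negative by Day 11) stop after one negative titer. The proportion with an event by Day 13 is (1 − s) × F(11); by Day 28 it is F(13).

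| s | By Day 13, mean 10 | By Day 13, mean 14 | Medians |
|---|---|---|---|
| 0% | 0.632 | 0.511 | 11 vs 13 |
| 20% | 0.506 | 0.408 | 13 vs 28 |
| 50% | 0.316 | 0.255 | 28 vs 28 |
| 80% | 0.126 | 0.102 | 28 vs 28 |

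Dated at the first negative of the pair, the medians are 9 (F(9) = 0.551) and 11 (F(11) = 0.511) at every s.

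**4. Effect on the hazard ratio.** Simulation, 20,000 per arm, unadjusted Cox model. Subjects with no negative titer by Day 13 are censored at Day 28, because one remaining swab cannot give two negatives. At s = 0 / 20 / 50 / 80%:

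- Breslow ties: about 1.37 / 1.33 / 1.29 / 1.25.
- Efron ties: between about 1.36 and 1.40 throughout.

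The SAP does not state its tie handling. The log-rank Z at 156 per arm moves from 2.39 to between 2.17 and 2.31.

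**The case against.** The strongest reply is that the practical effect may be small. Local testing is elective, and subjects who do not use it keep the every-other-day schedule. Section 7.2.8 asks for two consecutive local negatives and a further quantitative swab, which removes the delay when local tests coincide with swab days and the assays agree. The 20/50/80% shares are assumptions, and the true share could be near zero. The endpoint is one of 18 secondary endpoints; protocol 8.4 designates none as key and leaves the p-values uncorrected. All of this stands, and it limits the weight of the point.

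A reader might also infer that the fastest clearers become the slowest, so that a true treatment effect is largely erased. The documents do not support that. Under SAP 10.2.2, subjects with no negative titer by Day 13 are censored at Day 28, while affected early clearers with a negative Day 28 swab are events there. They still rank ahead, which is why the hazard ratio mostly survives.

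The reply does not remove the gap. The sequence in step 1 follows every rule and yields an event time 19 days late, and the SAP has no provision for it.

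**Conclusion.** The point holds for subjects who elect local testing and whose swabs stop before a second negative titer. SAP 10.2.2 then records at Day 28, or censors there, a clearance that would have been dated between Day 5 and Day 13 had swabs continued. The main harm is distorted event times and medians: under the assumed 10 vs 14 days, 11 vs 13 becomes 13 vs 28 at 20% affected and 28 vs 28 at 50% or more. Loss of treatment effect is modest with Breslow ties and close to nil with Efron.

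These sizes rest on the assumed clearance distribution, swab days, assay agreement and shares affected. The existence of the gap rests only on the documents. The primary endpoint, sample size and interim analysis are not touched. It should be corrected, but it does not threaten the trial's main conclusion.

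**What to change.** The SAP Addendum says enrollment has stopped and all enrolled patients have passed Day 28, so the swab schedule can no longer be changed. The repair lies in the analysis definition and should be made before unblinding.

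1. In SAP 10.2.2, date clearance at the first of two successive negative quantitative titers, with the second as confirmation even if taken on Day 28. Keep the second-negative date as a sensitivity analysis.
2. State how subjects with fewer than two negative titers after swabs stopped are handled, for example by interval censoring up to Day 28. Item 1 does not help those with no negative titer before the stop or with a missed Day 28 swab.
3. Reconcile footnote h with section 7.2.8 on whether one or two local negatives end the swabs, and on the extra swab.
4. State the tie handling for the Cox model, and report by arm how many subjects stopped swabs on local results.

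The cost is SAP wording and a short protocol clarification; no new data are needed. The downsides are that clearance times read about one swab interval earlier for everyone, and that a Day 28 swab may confirm a much earlier negative.

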## 1 BACKGROUND INFORMATION

For clarification purposes, the investigational product (IP) “BGE-175”, as identified in the Investigator’s Brochure (IB), is referred to as asapiprant hereafter in this document, unless otherwise noted. BGE-175-201 refers specifically to the protocol number (identifier) for this study.

Always refer to the latest version of the asapiprant IB for the overall benefit/risk assessment and the most accurate and current information regarding drug metabolism, pharmacokinetics (PK), efficacy, and safety of asapiprant.

### 1.1 Indication and Current Treatment Options

The effective treatment of COVID-19 remains an unmet medical need. Despite evolving treatments and intervention, mortality and morbidity associated with COVID-19 remains substantial, particularly in older patients, and there remains a clear need for novel treatments. To the best of our knowledge, there are no available treatments that address the clear deficits in the aging immune system that lead to accentuated morbidity and mortality.

Aging of the immune system increases COVID-19 severity, as seen in the exponential increase with age in hospitalizations and mortality in infected individuals. Compared to a 20-year-old with COVID-19, a 65-year-old is 5 times more likely to be hospitalized and 90 times more likely to die. An 85-year-old has even worse chances, with a 13 times higher risk of hospitalization and 630 times higher risk of death ([Centers for Disease Control and Prevention, 2020](#)). Age-related deficits in immune function that are already well understood in other infections like influenza, including reduced ability to mount an effective adaptive immune response, as well as an over-active innate immune response (macrophages and neutrophils), cause lung damage and lead to acute respiratory distress syndrome (ARDS) and mortality ([Chen et al., 2020](#); [Cunha et al., 2020](#); [Wu et al., 2020](#)). A therapy that specifically addresses the mechanisms underlying the age-dependence of COVID-19 severity is more likely to be effective in the most patients, and for those at highest risk of poor outcomes.

Building upon the existing safety database, this study will evaluate the efficacy of a novel oral small-molecule drug candidate in the highly vulnerable older patient population with COVID-19 infection that is inadequately served by the existing standard of care, resulting in high morbidity, disability, poor patient quality of life, and high costs to the healthcare system.

### 1.2 Investigational Product Asapiprant

#### 1.2.1 Product Background

Asapiprant, a small molecule in the D prostanoid (DP) receptor antagonist drug class, is a novel inhibitor of the prostaglandin D2 (PGD2) DP1 signaling pathway. This mechanism of action is immune modulating with the potential to treat respiratory infections and reduce further complication of respiratory distress. Asapiprant is being developed to treat COVID-19 based on observations in animal models of severe acute respiratory syndrome coronavirus (SARS-CoV) infection, previous human experience (different indication), and established manufacturing processes (tablet formulation).

## 1.2.2 Immunomodulation in the Prostaglandin D2(PGD2)-D Prostanoid (DP1) Signaling Pathway

PGD2-DP1 signaling inhibits an effective antiviral immune response via suppression of dendritic cell migration to draining lymph nodes as well as natural killer (NK) cell activation and interferon gamma (IFN- $\gamma$ ) production. The extent of this suppression strongly correlates with worse disease outcomes. This pathway is simultaneously dysregulated by immune aging and in COVID-19 patients. Older patients with COVID-19, as well as other patients at high risk for severe disease, have a less effective antiviral and adaptive immune response (via decreased dendritic cell and NK cell function), plus an exaggerated neutrophil response that results in increased tissue damage.

Furthermore, the mortality and morbidity of SARS-CoV-2 infection is largely mediated by damage to pulmonary tissue, which is infiltrated by excessive and ultimately damaging numbers of neutrophils. Although neutrophil activation is a normal component of the immune response to infection, COVID-19 patients exhibit neutrophil overactivation, exaggerated pulmonary inflammation, and cytokine storms leading to acute lung injury and death. Aging of the immune system is characterized by increased numbers of neutrophils and by nonspecific damage caused by overactive neutrophils that likely underlies much of the age-associated increase in mortality due to respiratory infections (Kulkarni et al., 2019; Li et al., 2014).

Modulation of PGD2-DP1 signaling has the potential to simultaneously boost the antiviral immune response against SARS-CoV-2 infection (mediated by dendritic cell and NK cells) while also reducing the nonspecific tissue damage caused by infiltration of neutrophils into the lungs of infected patients (Figure 2) (Jandl et al., 2016). Therefore, inhibition of PGD2-DP1 by asapiprant can potentially counteract age-related dysregulation of both the adaptive and innate immune systems and is expected to therapeutically benefit all COVID-19 patients, but most specifically older patients, who have the highest morbidity and mortality in this disease.

